## 1. Synopsis

**Protocol Title:**

A Phase 1 study of LY3434172, a bispecific antibody administered as a monotherapy in advanced solid tumors.

**Rationale:**

T-cells play a central role in immune response to tumor. However, tumors have adopted multiple mechanisms to evade host immune surveillance. One of the key mechanisms is the up-regulation of immune suppressive co-inhibitory molecules (immune checkpoint molecules) on the tumor cells. The programmed cell death protein-1 receptor (PD-1) axis is one of the dominant co-inhibitory pathways in T-cell activation. This axis involves three interactions. Both programmed death ligand 1 (PD-L1) and programmed death ligand 2 (PD-L2) ligands, expressed by antigen presenting cells (APC), can bind to PD-1 receptor on T-cells. In addition, PD-L1 can also bind to B7-1, which is upregulated along with PD-1 upon initial T-cell activation by antigen stimulation. These interactions lead to suppression of T-cell activation. In a variety of tumors, PD-L1 is frequently over-expressed by tumor cells, contributing to the immune tolerant state known as T-cell exhaustion. However, blocking the PD-1 axis has been shown to remove this suppression and reinvigorate T-cell activation.

While anti-PD-1 and anti-PD-L1 antibodies have demonstrated durable clinical responses in multiple tumor indications, only a subset of patients benefit from these treatments and there is room for further improvement. In vitro experiments have demonstrated that LY3434172 can bridge cells engineered to express PD-1 and those that express PD-L1. This enhances cell-based functional activity in vitro and antitumor efficacy in vivo compared to monoclonal antibody (mAb) monotherapy or combination; hence, the bispecific antibody (bsAb) may have the potential to improve upon the biological activity of existing PD-1 and PD-L1 agents, either alone or in combination. Clinical relevance of bridging is unknown at this time. The goal of this study is to establish the safety and recommended Phase 2 dose (RP2D) of LY3434172 administered as monotherapy to patients with advanced solid tumors.

## Objectives and Endpoints

Objectives	Endpoints
Primary	
To assess the safety and tolerability of LY3434172, thereby identifying a RP2D of LY3434172, administered to patients with advanced solid tumors.	
 
• DLTs
 
• Safety (including but not limited to): TEAEs, DLT-equivalent toxicities, SAEs, deaths, and clinical laboratory abnormalities per CTCAE (Version 5.0)
 

Secondary	
To assess the PK in patients with solid tumors of LY3434172.	
 
• AUC, <math>C_{\min}</math> and approximate <math>C_{\max}</math> of LY3434172
 

To assess preliminary antitumor activity a of LY3434172	
 
• ORR
 
• DOR
 
• TTR
 
• DCR
 

Abbreviations: AUC = area under the curve;  $C_{\max}$  = maximum serum/plasma concentration;  $C_{\min}$  = minimum serum/plasma concentration; CTCAE = Common Terminology Criteria in Adverse Events; DCR = disease control rate; DLT = dose-limiting toxicity; DOR = duration of response; ORR = objective response rate; PK = pharmacokinetics; RECIST = Response Evaluation Criteria in Solid Tumors; RP2D = recommended Phase 2 dose; SAE = serious adverse event; TEAE = treatment-emergent adverse event; TTR = time-to-response.

a Response assessment using RECIST 1.1 and RECIST 1.1 with confirmatory scan for disease progression.

## Overall Design:

Study J1E-MC-JZEA (JZEA) is a multicenter, nonrandomized, open-label Phase 1 study in patients with advanced solid tumors.

Phase 1 study will assess the safety and tolerability of LY3434172, administered as a monotherapy in patients with select advanced solid tumors. Study JZEA will facilitate a thorough safety evaluation and exploration of pharmacokinetics (PK) and pharmacodynamics effects CC1. Once dose-limiting toxicity (DLT) period is completed for respective Cohorts A1 to A5/6 up to approximately 12 to 15 additional patients may be added to two dose levels selected from these cohorts. For example, if 300mg is a dose level selected, additional patients may be enrolled in parallel with Cohort A5 after Cohort A4 has cleared DLT. Dose escalation will be driven by modified toxicity probability interval 2 (mTPI2) method, enrolling at least 3 patients per cohort.

In addition, an every three weeks (Q3W) dosing schedule (Cohorts A7 and A8) will be evaluated to allow for flexibility for future combinations with standard-of-care agents that may use a Q3W dose regimen. The Q3W dosing schedule could be initiated as Cohorts A7 and A8 in parallel with the Q2W expansion respectively.

Interim analyses will be conducted at the end of dose escalation from Cohort A1 to A5/6 at completion of DLT period across these cohorts. The RP2D will be identified after final analyses upon completion of this Phase 1 study.

**Number of Patients:**

Approximately 15 to 20 patients will be enrolled in Q2W dose escalation (Cohorts A1 to A6), approximately 12 to 15 additional patients may be added to two cohorts after dose level has cleared the DLT period. The sample size of Q3W depends primarily on PK profiles and clinical considerations.

**Treatment Arms and Duration:**

Patients enrolled in Phase 1 will receive LY3434172 monotherapy, as shown in the following table. Patients may continue to receive study treatment until they meet a criterion for discontinuation.

CCI

## 2. Schedule of Activities

[Table JZEA.1](#) presents the Baseline and On-study Schedule of Activities for all patients (for each of the 28-day cycle).

[Table JZEA.2](#) presents the Baseline and On-study Schedule of Activities for all patients (for each of the 21-day cycle).

[Table JZEA.3](#) presents the Post Treatment Follow-up Schedule of Activities for all patients (for each of the 21-day and 28-day cycle).

[Table JZEA.4](#) presents the Continued Access Schedule of Activities for patients receiving LY3434172.

Table JZEA.1 Baseline and On-Study Treatment Schedule of Activities (Cohort A1, A2, A3, A4, A5, and A6)

	Baseline (Day Relative to C1D1)		Cycle = 28 days								Instructions
			Cycle 1 (±3 days)		Cycle 2 (±3 days)		Cycle 3 (±3 days)		Cycle 4-n (±3 days)		
	≤28	≤7	D1	D15	D1	D15	D1	D15	D1	D15	
Procedure											
Informed consent	X										ICF must be signed before any protocol-specific procedures are performed
Inclusion/exclusion criteria	X										
Medical history	X										Including assessment of preexisting conditions and historical illnesses
Cancer treatment history	X										Record prior anticancer therapy
Concomitant medication	X		X								
 
At baseline, record prior and concurrent medications
 
Record all premedication, supportive care, and concomitant medication continuously at every visit and throughout the study
 

Physical examination	X		X	X	X	X	X	X	X	X	
 
D1 visit should be completed by a physician.
 
Should include palpable tumor measurement.
 

Vital signs	X		X	X	X	X	X	X	X	X	
Measure vital signs (height (at baseline), weight, temperature, blood pressure, pulse rate, oxygen saturation, and respiration rate) as follows (±5 minutes):
 
 
In Cycles 1 through 3: 
 
within 15 minutes prior to each LY3434172 infusion
 
every 15 minutes during each LY3434172 infusion
 
at the end of each LY3434172 infusion
 
 
 
 
A 4-hour observation period (See Section 5.1.1 and 7.4) following the end of LY3434172 administration will occur in Cycles 1 to 3.
 
 
every 30 (±5) minutes for the first hour and 60 (±5) minutes thereafter during the 4-hour observation period
 

	Baseline (Day Relative to C1D1)		Cycle = 28 days								Instructions
			Cycle 1 (±3 days)		Cycle 2 (±3 days)		Cycle 3 (±3 days)		Cycle 4-n (±3 days)		
	≤28	≤7	D1	D15	D1	D15	D1	D15	D1	D15	
											
 
In Cycle 4 and beyond, if the patient has not experienced an infusion-related reaction or other infusion-related AE: 
 
up to 15 minutes prior to each LY3434172 infusion
 
at least once during each LY3434172 infusion
 
at the end of each LY3434172 infusion
 
 
 

AE collection	X						X				
 
Collect continuously at every visit and throughout the study
 
CTCAE Version 5.0
 

ECOG PS	X		X	X	X	X	X	X	X	X	During study treatment, perform ≤3 days prior to D1 and D15 of each cycle.
ECHO	X									See Instructions	Perform locally, at baseline, Cycle 4 Day 1, and as clinically indicated
ECG											See Appendix 4 for ECG collection instructions
Blood tumor markers		X	X		X		X		X		As appropriate for particular tumor types (local testing). For example, include alpha-fetoprotein for patient with HCC.
Hematology		X	X	X	X	X	X	X	X	X	See Appendix 2
Coagulation	X										See Appendix 2 . Perform at baseline and as clinically indicated.
Fibrinogen	X										See Appendix 2 . Perform at baseline and as clinically indicated when CRP and/or ESR are elevated from baseline
TSH and free T4		X					X				See Appendix 2 . Perform at baseline, C3D1, every 2 cycles thereafter, and more frequently as clinically indicated.
C3a complement		X			X		X				See Appendix 2 . Perform at baseline, C2D1, C3D1, every other cycle thereafter and more frequently as clinically indicated.
C-ANCA/ P-ANCA		X									See Appendix 2 . Perform at baseline and more frequently as clinically indicated.

	Baseline (Day Relative to C1D1)		Cycle = 28 days						Instructions		
			Cycle 1 (±3 days)		Cycle 2 (±3 days)		Cycle 3 (±3 days)				
	≤28	≤7	D1	D15	D1	D15	D1	D15	D1	D15	
Troponin-I		X									See Appendix 2 . Perform at baseline and more frequently as clinically indicated.
Clinical chemistry		X	X	X	X	X	X	X	X		See Appendix 2
C-reactive protein		X	X		X		X		X		
ESR		X	X		X		X		X		
Urinalysis		X		X	X	X	X	X	X		See Appendix 2 . Perform at specified timepoint and as clinically indicated.
Pregnancy test		X	See Instructions						
 
• Applies only to women of childbearing potential
 
• Note: during study treatment, perform monthly or as required per local regulations and/or institutional guidelines.
 
• See Appendix 2
 
		
Tumor imaging/ assessment	X					X		See Instructions	
 
• Perform locally according to RECIST 1.1, using the same method at each assessment
 
• Perform as scheduled, even if study treatment is delayed or omitted, except when deemed not feasible in the opinion of the investigator because of the patient's clinical status
 
• Note: After C1D1, perform Q8W (±7 days) according to RECIST 1.1 for the first year, until a discontinuation criterion is met. If radiologic imaging verifies an initial assessment of PD, apply RECIST 1.1 with confirmatory scan for disease progression (Section 9.1.1).
 
• If the patient is still on study treatment after 1 year, perform tumor imaging approximately every 12W.
 
		
Sample collection									See Appendix 4 for pharmacodynamics, pharmacokinetics, immunogenicity, pharmacogenetics, tumor tissue, and other biomarkers.		

	Baseline (Day Relative to C1D1)		Cycle = 28 days						Instructions
			Cycle 1 (±3 days)		Cycle 2 (±3 days)		Cycle 3 (±3 days)		
	≤28	≤7	D1	D15	D1	D15	D1	D15	
Administer LY3434172			X	X	X	X	X	X	LY3434172 will be administered as an IV infusion over approximately 60 minutes, depending on dose level (doses <100 mg may require bolus IV injection administration over approximately 5 to 10 minutes). A 4-hour observation period following the end of LY3434172 administration will occur in Cycles 1 to 3.

Abbreviations: AE = adverse event; C = Cycle; C-ANCA = cytoplasmic antineutrophil cytoplasmic antibody; CRP = C-reactive protein; CTCAE = Common Terminology Criteria for Adverse Events; D = day; ECG = electrocardiogram; ECHO = echocardiogram; ECOG PS = Eastern Cooperative Oncology Group performance status; ESR = erythrocyte sedimentation rate; free T4 = free thyroxine; HCC = hepatocellular carcinoma; ICF = informed consent form; IV = intravenous; P-ANCA = perinuclear antineutrophil cytoplasmic antibody; PD = progressive disease; Q = every; RECIST 1.1 = Response Criteria in Solid Tumors Version 1.1; TSH = thyroid stimulating hormone; W = weeks.

Table JZEA.2 Baseline and On-Study Treatment Schedule of Activities (Cohort A7 and A8)

	Baseline (Day Relative to C1D1)		Cycle = 21 days						Instructions	
			Cycle 1 (±3 days)		Cycle 2 (±3 days)		Cycle 3 (±3 days)	Cycle 4-n (±3 days)		
	≤28	≤7	D1	D8	D1	D8	D1	D1		
Procedure										
Informed consent	X								ICF must be signed before any protocol-specific procedures are performed	
Inclusion/exclusion criteria	X									
Medical history	X								Including assessment of preexisting conditions and historical illnesses	
Cancer treatment history	X								Record prior anticancer therapy	
Concomitant medication	X								
 
At baseline, record prior and concurrent medications
 
Record all premedication, supportive care, and concomitant medication continuously at each visit and throughout the study.
 
	
Physical examination	X		X	X	X	X	X	X	
 
D1 visit should be completed by a physician.
 
Should include palpable tumor measurement.
 
	
Vital signs	X		X		X		X	X	
Measure vital signs (height (at baseline), weight, temperature, blood pressure, pulse rate, oxygen saturation, and respiration rate) as follows (±5 minutes):
 
 
In Cycles 1 through 3: 
 
up to 15 minutes prior to each LY3434172 infusion
 
every 15 minutes during each LY3434172 infusion
 
at the end of each LY3434172 infusion
 
 
 
 
A 4-hour observation period (See Section 5.1.1 and 7.4) following the end of LY3434172 administration will occur in Cycles 1 to 3.
 
 
every 30 (±5) minutes for the first hour and every 60 (±5) minutes thereafter during the 4-hour observation period.
 
	

	Baseline (Day Relative to C1D1)		Cycle = 21 days					Instructions	
			Cycle 1 (±3 days)		Cycle 2 (±3 days)		Cycle 3 (±3 days)	Cycle 4-n (±3 days)	
	≤28	≤7	D1	D8	D1	D8	D1	D1	
									
 
In Cycle 4 and beyond, if the patient has not experienced an infusion-related reaction or other infusion-related AE: 
 
up to 15 minutes prior to each LY3434172 infusion
 
at least once during each LY3434172 infusion
 
at the end of each LY3434172 infusion
 
 
 

AE collection	X				X				
 
Collect continuously at each visit and throughout the study
 
CTCAE Version 5.0
 

ECOG PS	X		X	X	X	X	X	X	During study treatment, perform ≤3 days prior to D1 of each cycle.
ECHO	X							See instructions	Perform locally, at baseline, at Cycle 4 Day 1, and as clinically indicated.
ECG									See Appendix 4 for ECG collection instructions
Blood tumor markers		X	X		X		X	X	As appropriate for particular tumor types (local testing). For example, include alpha-fetoprotein for patients with HCC.
Hematology		X	X	X	X	X	X	X	See Appendix 2
Coagulation	X								See Appendix 2 . Perform at baseline and as clinically indicated.
Fibrinogen	X								See Appendix 2 . Perform at baseline and as clinically indicated when CRP and/or ESR are elevated from baseline
TSH and free T4		X					X		See Appendix 2 . Perform at baseline, C3D1, every 2 cycles thereafter, and more frequently as clinically indicated.
C3a complement		X			X		X		See Appendix 2 . Perform at baseline, C2D1, C3D1, every other cycle thereafter and more frequently as clinically indicated.
C-ANCA/P-ANCA		X							See Appendix 2 . Perform at baseline and more frequently as clinically indicated.

	Baseline (Day Relative to C1D1)		Cycle = 21 days					Instructions	
			Cycle 1 (±3 days)		Cycle 2 (±3 days)		Cycle 3 (±3 days)	Cycle 4-n (±3 days)	
	≤28	≤7	D1	D8	D1	D8	D1	D1	
Troponin-I		X							See Appendix 2 . Perform at baseline and more frequently as clinically indicated.
Clinical chemistry		X	X	X	X	X	X	X	See Appendix 2
C-reactive protein		X	X		X		X	X	
ESR		X	X		X		X	X	
Urinalysis		X		X	X	X	X	X	See Appendix 2 . Perform at specified timepoint and as clinically indicated.
Pregnancy test		X	See Instructions					
 
Applies only to women of childbearing potential
 
Note: during study treatment, perform monthly or as required per local regulations and/or institutional guidelines
 
See Appendix 2
 
	
 
Applies only to women of childbearing potential
 
Note: during study treatment, perform monthly or as required per local regulations and/or institutional guidelines
 
See Appendix 2
 

Tumor imaging/ assessment	X					X	See Instruc tions		
Sample collection								See Appendix 4 for pharmacodynamics, pharmacokinetics, immunogenicity, pharmacogenetics, tumor tissue, and other biomarkers.	

	Baseline (Day Relative to C1D1)		Cycle = 21 days					Instructions	
			Cycle 1 (±3 days)		Cycle 2 (±3 days)		Cycle 3 (±3 days)	Cycle 4-n (±3 days)	
	≤28	≤7	D1	D8	D1	D8	D1	D1	
Administer LY3434172			X		X		X	X	LY3434172 will be administered as an IV infusion over approximately 60 minutes, depending on dose level (doses <100 mg may require bolus IV injection administration approximately 5 to 10 minutes). A 4-hour observation period following the end of LY3434172 administration will occur in Cycles 1 to 3.

Abbreviations: AE = adverse event; C = Cycle; C-ANCA = cytoplasmic antineutrophil cytoplasmic antibody; CTCAE = Common Terminology Criteria for Adverse Events; D = day; ECG = electrocardiogram; ECHO = echocardiogram; ECOG PS = Eastern Cooperative Oncology Group performance status; ESR = erythrocyte sedimentation rate; free T4 = free thyroxine; HCC = hepatocellular carcinoma; ICF = informed consent form; IV = intravenous; P-ANCA = perinuclear antineutrophil cytoplasmic antibody; PD = progressive disease; Q = every; RECIST 1.1 = Response Criteria in Solid Tumors Version 1.1; TSH = thyroid stimulating hormone; W = weeks.

Table JZEA.3. Poststudy Treatment Schedule of Activities (All Parts)

Visit	Follow-Up Visit ( $\pm 7$ days)				Instructions	
	Short-Term a			Long-Term (Q90D) b		
	30-Day	60-Day	90-Day			
Procedure	801	802	803	804 to 8XX		
Pregnancy test	X	X	X		Perform pregnancy test for women of childbearing potential	
ECG					See Appendix 4 for ECG collection instructions	
Physical examination	X				Including weight and vital signs (temperature, blood pressure, pulse rate, oxygen saturation, and respiration rate)	
Concomitant medication	X					
AE collection	X	X	X	X	CTCAE Version 5.0. During the 30-, 60-, and 90-day follow-up visits, collect all AEs/SAEs. Thereafter, collect only SAEs related to study treatment or protocol procedures	
ECOG performance status	X					
Tumor imaging/assessment		X			For patients who discontinue study treatment without objectively measured PD, continue to perform tumor assessment and imaging every 8 to 12 weeks according to the standard-of-care	
Collection of survival information	X	X	X	X	In-person office visits are not required; the site may confirm survival by contacting the patient directly via telephone or other means of communication (for example, email)	
Collection of poststudy-treatment anticancer therapy information	X	X	X	X	Discontinuation from study treatment must occur prior to introduction of the new agent	
Hematology	X				See Appendix 2	
Clinical Chemistry	X				See Appendix 2	
Coagulation	X				See Appendix 2	
Sample collection					See Appendix 4 for pharmacodynamics, pharmacokinetics, immunogenicity, pharmacogenetics, tumor tissue, and other biomarkers.	

Abbreviations: AE = adverse event; CTCAE = Common Terminology Criteria for Adverse Events (NCI 2017); ECG = electrocardiogram; ECOG = Eastern Cooperative Oncology Group (Oken et al. 1982); F/U = follow-up; PD = progressive disease; PK = pharmacokinetics; SAE = serious adverse event.

a Short-term follow-up begins when the patient and investigator agree that the patient will discontinue study treatment and ends on the day of the 90-day ( $\pm 7$  days) follow-up visit.

b Long-term follow-up begins when short-term follow-up is completed and continues until death, study withdrawal, or the patient is lost to follow-up. No follow-up procedures will be performed for a patient who withdraws informed consent unless he or she has explicitly provided permission and consent.

Table JZEA.4. Continued Access Schedule of Activities

	Continued Access Treatment		Continued Access Follow-up Visits a			Instructions:
			30-Day	60-Day	90-Day	
Visit	501-5XX		901	902	903	
	D1	D15				
LY3434172 Schedule	All	Q2W				
Procedure						
AE collection	X	X	X	X	X	As part of AE collection, monitor vital signs and perform standard laboratory tests (hematology, chemistry, urinalysis, and pregnancy testing) at the same frequency as the study treatment period (see Table JZEA.1 and Table JZEA.2 ). All laboratory tests during the continued access period will be performed in the local laboratories only.
PK, IG and exploratory hypersensitivity						In the event of an IRR, blood samples will be collected for PK, IG and exploratory hypersensitivity analyses at the following time points, as close as possible to: (i) the onset of the IRR, (ii) the resolution of the IRR, and (iii) 30 [ $\pm 3$ ] days following the IRR. CCI  [REDACTED]  [REDACTED]  [REDACTED]
Administer LY3434172	X	X				

Abbreviations: AE = adverse event; D = day; IG = immunogenicity; IRR = infusion-related reaction; PK = pharmacokinetics.

a Continued access follow-up begins when the patient and the investigator agree that the patient will no longer continue treatment in the continued access period and lasts approximately 30 days.

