### 5.1.1. Dose Escalation

The first patient will be enrolled in Cohort A1 and treated according to a Q2W dosing regimen (see [Figure JZEA.1](#)). CCI

A DLT

observation period of 28 days (42 days in Cohort A1) will apply to all patients on the Q2W dosing regimen in subsequent cohorts. Ongoing safety reviews between the Lilly clinical research physician/clinical research scientist (CRP/CRS) and the investigators will be conducted during and upon completion of the DLT period for each cohort, to ensure it is safe to continue with the next dose-escalation cohort.

After the first patient in Cohort A1 receives the first dose of LY3434172, there will be a delay of 1 week before the second patient receives LY3434172 to allow for safety observation. In all subsequent cohorts, the first patient in each dose level will be observed for approximately 24 hours before any additional patients are treated; no additional delays are required for subsequent patients in the same cohort.

Patients in Cohorts A2, A3, A4, A5, and A6 (optional), respectively, CCI provided safety is established in the preceding cohorts. Once DLT period of 28 days for Q2W, except Cohort A1 with 42 day DLT, is completed for respective dose levels within Cohorts A1 to A5/A6, two dose

levels, yet to be determined but will be selected from these cohorts, can be expanded between 12 and 15 patients in total. Pharmacokinetic, pharmacodynamic and safety data evaluated during the course of the dose escalation will be used to select these two dose levels. The purpose of expanding to additional 12-15 patients is to further inform safety, PK and pharmacodynamics. These cohorts will continue to enroll while interim analysis (IA) is ongoing.

Cohorts of patients will be treated with escalating doses of LY3434172 according to an mTPI-2 method until the criteria for reaching the maximum-tolerated dose (MTD) are met. For some immuno-oncology compounds that have manageable safety profiles and do not reach a MTD, additional information such as pharmacodynamic markers may be helpful in determining the appropriate RP2D (Agrawal et al. 2016; Parchment et al. 2016).

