### 7.2.2.2. Dose-Limiting Toxicity Determination

A DLT is defined as any of the events listed in [Table JZEA.8](#), if both the following criteria are met:

- the event occurs during the DLT observation period (Cycle 1, 42 days) for Cohort A1, (Cycle 1, 28 days) for Cohorts A2 to A5 (A2 to A6 if Cohort A6 is opened), (Cycle 1 and 2, 42 days) for Cohorts A7 and A8, and
- the event is clinically significant and definitely, probably, or possibly related to LY3434172, in the opinion of the investigator.

Patients in Cohorts A1 to A5/6, A7, and A8 who experience a DLT in Cycle 1 will be discontinued from study treatment.

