**Table JZEA.8. Dose-Limiting Toxicity**

Hematologic toxicity

 
Grade 3 thrombocytopenia associated with clinically significant bleeding and requiring platelet transfusion or Grade 4 thrombocytopenia of any duration
 
Grade <math>\geq 3</math> febrile neutropenia
 
Grade <math>\geq 3</math> anemia requiring a blood transfusion
 
Other Grade 4 toxicity lasting <math>>7</math> days, excluding toxicities listed in Section 7.2.2.1
 

Nonhematologic toxicity – nonlaboratory

 
Grade 4 irAE, except as stated otherwise below
 
Grade <math>\geq 3</math> colitis or noninfectious pneumonitis
 
Other Grade 3 irAE, excluding colitis or pneumonitis, that: 
 
does not downgrade to Grade 2 within 3 days after onset of the event despite optimal medical management including corticosteroid therapy, or
 
does not downgrade to Grade <math>\leq 1</math> or the patient's baseline level within 14 days after onset of the event
 
 
 
Grade <math>\geq 3</math> pneumonitis or Grade 2 pneumonitis that does not show clinical improvement within 3 days after initiation of optimal medical management including corticosteroids therapy, which is then treated as Grade 3
 
Grade <math>\geq 3</math> toxicity despite optimal supportive care (e.g., nausea, vomiting, and diarrhea)
 
Grade <math>\geq 3</math> fatigue lasting <math>>7</math> days
 
Grade <math>\geq 3</math> hypertension despite maximal medical therapy
 

Nonhematologic toxicity – laboratory/investigations

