**Pharmacokinetic, Immunogenicity, Biomarker, and ECG Collection Time Points**  
**Cohorts with Q2W Dosing (Cohort A1, A2, A3, A4, A5, and A6)**

Pharmacokinetic, Immunogenicity, Biomarker, and ECG Collection Time Points Cohorts with Q2W Dosing (Cohort A1, A2, A3, A4, A5, and A6)													
Cycle/Day	Study Day	Sample Time (Relative to the END of LY3434172 Infusion)	PK a	IG a	Whole Blood (PGx)	Biomarker Collection						ECG	
						Plasma	Ex vivo	Whole Blood & PBMC b	Serum	Tissue	sPD-1 and sPD-L1		
Baseline		≤28 days prior to C1D1  • ECG: 2-3 sets of ECGs (each set is a triplicate), with approximately 15 minutes between each set. d Tumor tissue: required see Section 9.8.1.								X		X	X
Baseline		≤7 days prior to C1D1					X	X					
C1D1	1	• 0 hour predosee • PK, IG, and biomarkers • ECG: 2-3 sets of ECGs (each set is a triplicate), with approximately 15 minutes between each set. d Before blood draw.	X	X	X	X	X	X	X		X	X	
C1D1		• 1 hour post LY3434172 infusionf • ECG (triplicate) Before blood draw. d	X				X	X	X		X	X	

Pharmacokinetic, Immunogenicity, Biomarker, and ECG Collection Time Points Cohorts with Q2W Dosing (Cohort A1, A2, A3, A4, A5, and A6)												
Cycle/Day	Study Day	Sample Time (Relative to the END of LY3434172 Infusion)	PK a	IG a	Whole Blood (PGx)	Biomarker Collection						
						Plasma	Ex vivo	Whole Blood & PBMC b	Serum	Tissue	sPD-1 and sPD-L1	Stool c
C1D1	1	
 
• 3 hours post LY3434172 infusionf
 
• ECG (triplicate) Before blood drawd
 
	X					X	X		X	
C1D2	2	
 
• 24 hours post LY3434172 infusionf
 
• ECG (triplicate) Before blood draw.d
 
	X				X	X	X		X	X
C1D4	4	72 hours post LY3434172 infusion f	X								X	
C1D8	8	168 hours post LY3434172 infusion f	X	X		X	X	X	X		X	
C1D15	15	
 
• 0 hour predosee
 
• PK, IG, and biomarkers
 
	X	X			X	X	X		X	
C1D15	15	
 
• 1 hour post LY3434172 infusionf
 
• ECG (triplicate) Before blood draw.d
 
	X				X (only cohort A1)		X (only A1)		X	X

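### Q2W Cohorts A2 to A5/A6 have one scheduled post-dose hematology and chemistry panel inside the 28-day DLT window, so short, symptom-free laboratory DLTs can go uncounted

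*Protocol*

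**What the plan says.** **Windows.** Protocol Section 7.2.2.2 sets the DLT observation period as "Cycle 1, 42 days) for Cohort A1, (Cycle 1, 28 days) for Cohorts A2 to A5" (to A6 if that cohort opens).

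**Q2W safety blood tests.** The schedule headed "Table JZEA.1 Baseline and On-Study Treatment Schedule of Activities (Cohort A1, A2, A3, A4, A5, and A6" gives each cycle a D1 and a D15 column, with visits ±3 days. The hematology row, "Hematology X X X X X X X X X See", has one baseline mark and then one per column. Clinical chemistry has the same Cycle 1 marks. Appendix 4 numbers C2D1 as Day 29 and C2D15 as Day 43.

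**First-patient observation.** In Cohort A1, Section 5.1.1 says that "there will be a delay of 1 week before the second patient receives LY3434172 to allow for safety observation". Later cohorts have about 24 hours.

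**Other Q2W visits.** Appendix 4 also brings patients in on Days 2, 4, 8, 16 and 22. The Day 8 entry is "168 hours post LY3434172 infusion". These visits take PK, immunogenicity and biomarker samples, with ECGs on some days, but no hematology or chemistry.

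**Endpoint.** Table JZEA.8 includes laboratory DLTs without a duration requirement:
- "Grade 4 thrombocytopenia of any duration"
- ALT or AST >8 × ULN without HCC or liver metastasis
- ALT or AST >3 × ULN with bilirubin >2 × ULN and no cholestasis
- total bilirubin >3 × ULN

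Under Section 7.2.2.2 the event must also be judged clinically significant and at least possibly related.

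**The concern.** DLTs are a primary endpoint and the input to the mTPI-2 grid. Where a criterion is met by a single value, it can be counted only if blood is drawn while the value is abnormal. Between Day 1 and Day 15, and again between Day 15 and Day 29, the Q2W schedule does not look. Day 15 is also the second dosing visit, so at nominal dates no panel is scheduled after that visit and inside the 28-day window.

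The error runs one way. Under Section 7.6.1.1 a patient with no recorded DLT who has received all assigned doses is DLT evaluable. An unseen event is therefore counted as a non-event rather than as missing, and the observed DLT rate falls. At the small cohort sizes planned, one patient can change the grid's decision.

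The A1 pause is a separate point. Its stated purpose is safety observation, yet no hematology or chemistry is scheduled within it, although the patient is bled on Days 2, 4 and 8 for other purposes.

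**Working it through.** **1. The plan's own grid.** Appendix 8 gives 0/3 = E, 1/3 = S, 1/6 = E and 2/6 = S. All four are reproduced by mTPI-2 with target 30% and equivalence interval 25–35%. This uses a Beta(1,1) prior, sub-intervals 0.10 wide and a 0.95 cutoff for DU, which are assumptions because the documents do not state them. One unseen DLT changes the decision as follows:

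| n | True count | Read as | Decision |
|---|---|---|---|
| 3, 4 | 1 | 0 | S becomes E |
| 5 | 2 | 1 | D becomes E |
| 6, 7, 8 | 2 | 1 | S becomes E |

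**2. Panel count at nominal dates.**
- A2 to A5/A6, 28 days: Day 15 only. Day 29 is one day after the window; with ±3 days it can fall on Days 26 to 32.
- A1, 42 days: Days 15 and 29. C2D15 is Day 43.
- A1 one-week pause: none.

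**3. Chance that a silent event is seen.** Assume onset equally likely on each of Days 2 to 28 (27 days), a fixed duration of L days and no unscheduled draws. An event is seen if some draw day d satisfies onset ≤ d < onset + L. Day 29 is counted, in the schedule's favour.

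| L (days) | Day 15 only | Days 15, 29 | Days 8, 15, 22, 29 |
|---|---|---|---|
| 3 | 3/27 = 11% | 5/27 = 19% | 11/27 = 41% |
| 5 | 5/27 = 19% | 9/27 = 33% | 19/27 = 70% |
| 7 | 7/27 = 26% | 13/27 = 48% | 27/27 = 100% |
| 10 | 10/27 = 37% | 19/27 = 70% | 27/27 = 100% |
| 14 | 14/27 = 52% | 27/27 = 100% | 27/27 = 100% |

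For L = 7, the Day 15 draw catches onset on Days 9 to 15 and the Day 29 draw catches Days 23 to 28: 7 + 6 = 13.

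**4. The same with visit windows.** Let Days 15 and 29 vary uniformly by ±3 days (Table JZEA.1), and Days 8 and 22 by ±1 day (the ±24 hours in Appendix 4). A 7-day event is then seen in 47% of cases now and 87% with the added panels (70% at the worst combination of days). A 3-day event is seen in 17% and 40%.

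**5. Effect on the escalation decision.** Let p be the true DLT rate, s the share of DLTs that are silent and laboratory-only, and m the chance of missing one. The observed rate is q = p(1 − s·m). At n = 3 only 0/3 gives E, so P(escalate) = (1 − q)³.
- All DLTs seen, p = 0.30: 0.70³ = 0.343.
- s = 0.10, L = 7, Days 15 and 29: m = 14/27 = 0.519, q = 0.2844, P = 0.366.
- s = 0.10, L = 3, Days 15 and 29: m = 22/27 = 0.815, q = 0.2756, P = 0.380.
- s = 0.25, L = 7, Days 15 and 29: q = 0.2611, P = 0.403.
- s = 0.25, L = 3, Day 15 only: m = 24/27 = 0.889, q = 0.2333, P = 0.451.

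With Days 8 and 22 added, at nominal days and s = 0.25, P is 0.343 for 7-day events and 0.413 for 3-day events.

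**The case against.** **Judgement is part of the definition.** Crossing a threshold is not enough: the investigator must also find the event clinically significant and at least possibly related. A brief, symptom-free abnormality is where that judgement is least certain. Other laboratory criteria need persistence (over 72 hours, 7 days or 14 days), symptoms or intervention. This stands, and it limits the point to what *can* be missed. A reader might infer that DLTs *are* being missed; the documents give no rate to support that.

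**Other safeguards exist.** Adverse events are collected continuously, local chemistry is allowed if clinically indicated, safety reviews run during the DLT period, and the sponsor and investigators may be more conservative than the grid. These help with symptomatic events. A silent abnormality gives no trigger for an extra test, and a review cannot act on a value nobody measured.

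**The pause and the 28-day window belong to different cohorts.** A reader might combine them into one gap. The one-week pause is A1's alone, and A1 has a 42-day window with two panels. Section 5.1.1 is also partly redacted, so a rationale may exist that is not visible.

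**The step from stay to escalate.** From step 3 one could say that escalation replaces stay in 14/27 = 52% of 3-patient cohorts. That figure presupposes that exactly one silent 7-day DLT has occurred. It is not a rate of wrong decisions; step 5 is the relevant quantity.

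**The Q3W comparison.** Table JZEA.2 has Day 8 panels in Cycles 1 and 2, so adding Day 8 to Q2W might seem to align the two schedules. It does not. Q3W panels fall on Days 8, 22, 29 and 43, which also leaves 14-day gaps. With onset over Days 2 to 42, they see 27/41 = 66% of 7-day events. Q2W would move from 48% to above that figure, so a difference between schedules would remain.

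**Conclusion.** The point holds, as a weakness in how the primary endpoint is ascertained. It is not a contradiction that invalidates the design. In Cohorts A2 to A5/A6 a single scheduled panel falls inside the 28-day window at nominal dates, while some DLT criteria can be met by one value. About half of silent 7-day events, and more than four in five silent 3-day events, would not be seen. At nominal days nothing is gained for events of 14 days or more once Day 29 is counted.

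The effect on escalation is modest unless silent laboratory DLTs are common: from 0.343 to 0.37–0.38 if they are 10% of DLTs, and to 0.40–0.45 if they are 25% (n = 3, true rate 30%, events of 3 to 7 days). Onset pattern, duration and silent share are all assumptions. The complete detection of 7-day events with added panels at nominal days should not be quoted as the expected gain; with visit windows it is about 87%.

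For A1 the finding is narrower: the pause is described as safety observation, but no hematology or chemistry is scheduled in it.

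**What to change.** - Add hematology and clinical chemistry to Table JZEA.1 at C1D8 and C1D22, using the blood-draw visits already in Appendix 4. State whether chemistry there is read locally as well as centrally: Appendix 2 makes central testing the requirement but bases treatment decisions on local results.
- Reconcile Section 5.1.1 with Table JZEA.1 on what laboratory information the A1 pause is meant to provide. The Day 8 sample has a ±24-hour window and may fall after the week has ended.

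**Cost.** Two extra panels per Q2W patient at existing visits, plus data entry, and possibly a slightly higher observed DLT rate. No dose, treatment or escalation rule changes.
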